The patients within primary care teams randomized to the Goals for Eating and Moving (GEM) intervention will have greater weight loss than those who receive Enhanced Usual Care.

Research Design

- a. We will conduct a cluster-randomized controlled trial of the GEM intervention at two healthcare systems in New York City: The VA New York Harbor Healthcare System (Manhattan campus) and Montefiore Medical Groups (4 sites affiliated with New York City Research and Improvement Networking practice-based research network).
- b. We will conduct a RE-AIM (reach, efficacy, adoption, implementation, and maintenance) evaluation of the GEM intervention.²⁰
- c. We will explore potential effects of secondary measures such as perceived procedural fairness or experiences of discrimination on health outcomes and weight-loss behaviors including but not limited to dietary behaviors, physical activity, and quality of life measures.

Background

Modest weight loss (7%) via the Diabetes Prevention Program (DPP) can reduce the risk of diabetes in high-risk patients by 58%.³ Similarly, all Veterans Affairs (VA) Medical Centers offer the MOVE! program, a lifestyle-based program delivered in small group sessions.^{4, 26, 27} One report found that patients who attended two or more MOVE! sessions were more likely than matched controls to have clinically significant (>5%) weight loss and less likely to gain weight.²⁸ Unfortunately, intensive lifestyle programs like this are not available to most primary care patients and very few studies have looked at interventions to treat obesity in the primary care setting,²⁹⁻³⁰ despite the obvious need for improving delivery of obesity care. We need to test more robust strategies to increase participation in these effective programs.

The primary care setting is critical to reducing the burden of obesity. Primary care (PC) is an important venue to promote weight loss through lifestyle behavior change, and effective PC-based interventions can potentially have a significant public health impact,

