- Participated in MOVE!, DPP, or another intensive weight management program (>4 sessions) in the past year,
- Have a history of bariatric surgery,
- Are pregnant, breastfeeding or become pregnant during the intervention period,
- Have a provider who states they should not participate,
- Have self-reported inability to read at 5th grade level.
- Currently take weight-loss medications or diabetes medication that may impact weight change
- Receive chemotherapy or cancer treatment
- Had metastatic cancer in the last 6 months
- Does not want to lose weight

We are excluding individuals with any of the above listed conditions as this will likely impact their ability to fully participate in this study. Additionally, some of these listed health conditions may limit physical activity. As this intervention includes telephone weight management counseling and reviewing of printed weight management materials, we are excluding participants without a telephone or participants who cannot read material written at the 5th grade level or above.

We will use phone screen and EHR information to verify inclusion and exclusion criteria.

Vulnerable Subjects

No vulnerable populations will be included as part of this weight management intervention study.

III. Methods and Procedures

[figure not shown]
We will conduct a cluster-randomized controlled trial of the GEM intervention at two healthcare systems in New York City: The VA New York Harbor Healthcare System (Manhattan campus) and Montefiore Medical Group (4 sites affiliated with New York City Research and Improvement Networking (NYC RING) practice-based research network. Participants will be randomized at the team level (19 teams with approximately 28 providers and 512 patients to achieve a sample size of 384 patients at 12 month follow-up for the primary outcome assessment). The primary care teams will be randomized using a random number generator (block randomization with block size of four) to either the GEM Intervention or Enhanced Usual Care arms. Randomization will be stratified by healthcare system (MMG and VA).

Intervention Arm – GEM

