- Encourage participation (using MI) in MOVE, DPP, or community-based programs/gyms
- Teach how to self-monitor weight, diet, and PA behaviors via pedometer, food log, and/or weight management apps (e.g. MOVE! Coach mobile^{70,71} on iPhones, My Fitness Pal⁷² on Androids)

- Provide brief MI and Brief Action Planning⁷³ to address barriers and increase patient self-efficacy
- Facilitate meetings with extended team members (e.g. health educators, dietitians, primary care physicians) if needed
- Enter a report for primary care teams into EHR from the GEM tool
- Communicate potential barriers/concerns to the team at baseline visit and as needed throughout the intervention period (e.g., via EHR notes, secure messaging system, telephone, and/or team meetings)
- ❖ **Telephone Coaching:** To achieve sufficient intensity according to USPSTF guidelines,¹⁰ we will incorporate 12 telephone coaching calls by a health coach over 12 months. Scheduled calls will occur every 2 weeks (biweekly) for months 1–3, monthly for months 4–6, and every other month (bimonthly) for months 7–12. GEM Intervention arm patients will receive a reminder call or an electronic reminder via MyHealtheVet or VA's Annie texting service to self-monitor their weight, food intake, and PA for at least 3 days prior to the coaching call. Studies suggest that episodes of short, consistent self-monitoring (for 3 days) reduce weight and may improve adherence.⁷⁴ Health coaches will use self-reported self-monitoring data (from pedometers, food logs, and smart phone apps) to determine goal adherence and counsel patients to encourage small changes.⁴⁹ Health coaches will document sessions in REDCap, help patients create new goals when appropriate, and use MI techniques to address barriers to behavior change. Patients will be able to contact health coaches via telephone for additional support. Patients will be reminded to discuss their goals during their next primary care visit (if scheduled).
- ❖ **Provider Role:** Providers in the GEM arm will provide 3–5 minutes of counseling, use clinical reminders to document this counseling, provide brief MI to address barriers (depending on time and patient needs), and discuss GEM-generated weight management goals during future visits. The GEM tool creates a report to communicate data to the participant's primary care team and generates a clinical reminder which facilitates documentation of primary team goal setting conversations and counseling.

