Control Arm – Enhanced Usual Care (EUC)

Patients in the EUC arm will receive non-tailored weight management handouts by health coaches (Health Bulletins from the NYC DOHMH).^{79–81} Patients will follow-up with their primary care teams as needed.

Data Collection

Patients: Assessment will occur at the following time points:

- ❖ At Baseline, 6, 12, and 24 months, patients will meet in-person or over the phone (for follow-up) with a research assistant (RA) to complete surveys; measure weight, height, blood pressure, and waist circumference. Baseline surveys will include a pre-survey (completed before receiving GEM Intervention/Enhanced Usual Care). Electronic chart review will also occur at these time points. The RA will administer all surveys and enter the data directly into our REDCap database. To compensate for

travel and time spent completing study measurements, patients will be given \$25 dollars for the baseline study visit, \$30 dollars for the 6-month study visit, \$40 dollars for the 12-month study visit, and \$50 for the follow-up 24-month visit and \$20 dollars for the optional one hour opinion session and 2 follow-up phone calls. During the baseline visit we will encourage patients to sign-up for MyHealtheVet, if they haven't done. In addition, we will inform patients about the VA's secure Annie texting service and help them to sign up, if requested, as another option to receive reminder text messages for appointmentsIf patients are signed-up for MyHealtheVet, they can choose to receive reminders for their upcoming study visits or health coach phone calls electronically via myHealtheVet. Alternatively, patients can choose receive reminder phone calls from secure VA phones lines or via the secure Cisco Jabber application.. Before upcoming phone coaching calls and study visits, we will send reminders via the secure messaging system MyhealtheVet, VA's Annie texting service or make phone calls via secure VA phone lines or via the secure Cisco Jabber application.

- ❖ When performing telephone Coaching Calls (patients in GEM Intervention arm only), Health coaches will use a counseling tool that also facilitates data collection into REDCap database.
- ❖ Chart reviews 12 and 24 months post-baseline visit to explore maintenance of counseling post-intervention

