Impact of the GEM intervention on weight change, and clinical and behavioral outcomes:

The primary outcome is mean weight loss at 12 months. Mann-Whitney tests for continuous outcomes (e.g., weight loss) and Fisher's exact tests for categorical outcomes (e.g., whether or not patients achieve $\geq 5\%$ weight loss) will be used to compare the two intervention arms at 12 months. Unadjusted confidence intervals will be computed to compare the effects of the GEM intervention on outcomes with the effects of enhanced usual care on outcomes. Moreover, we will use repeated measures modeling, based on mixed models, to compare outcome variables between intervention arms, using all the data at baseline and three follow-up visits. Such modeling can adjust for baseline characteristics (e.g. diabetes, gender), taking into account: a) the correlation among patients within providers, and b) the correlation among repeated measures within patients. Model-based adjusted confidence intervals will be provided to also measure the effects of the intervention on outcomes. Although the repeated measures modeling can address missing data automatically, assuming it is missing at random, we will further use a multiple imputation procedure to conduct sensitivity analyses under the assumption of missing data not at random. The sensitivity analyses will use pattern-mixture models to examine if the statistical findings are robust across several scenarios, including the least-favorable scenario where the missing data from the GEM intervention arm follows the same pattern as that of the observed data from the usual care arm.

Predictors of weight loss in the GEM intervention arm related to: a) goal setting processes and b) intervention components: We will use visualization tools, such as scatterplots and descriptive analyses (e.g., Spearman correlation coefficients) to display the association between weight change and potential predictors. Multivariate regression models will be used to examine the effects of those predictors, which we suspect will be associated with weight loss in the intervention arm. Multivariate linear regression models will be considered for continuous outcomes and multiple logistic regression models will be considered for binary outcomes. Missing data will be dealt with using inverse-probability-weighted methods.

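### The mixed model allows for correlation within providers but not within teams, the randomised unit, so its intervals for the 12-month effect can be too narrow

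*Combined protocol and SAP*

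**What the plan says.** The Hypothesis section is framed by team: "The patients within primary care teams randomized to the Goals for Eating and Moving (GEM) intervention will have greater weight loss" than those under Enhanced Usual Care. Section III (Methods and Procedures) makes the team the unit of allocation: "Participants will be randomized at the team level (19 teams with approximately 28 providers and 512 patients", with 384 patients expected at 12 months. Teams are allocated in blocks of four, stratified by healthcare system.

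Section VI (Method of Subject Identification and Recruitment) counts 19 teams, 11 at the VA and 8 at Montefiore, and has two to three providers recruited per team before randomisation. The introductory design summary gives 16 teams.

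The Data Analysis section takes mean weight loss at 12 months as the primary outcome. It first lists Mann-Whitney and Fisher tests and unadjusted intervals, none of which mentions clustering. It then adds a mixed model "using all the data at baseline and three follow-up visits", "taking into account: a) the correlation among patients within providers, and b) the correlation among repeated measures within patients", and states: "Model-based adjusted confidence intervals will be provided to also measure the effects of the intervention on outcomes". The text available for review contains no team random effect, no team-level robust variance and no degrees of freedom based on teams.

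**The concern.** Providers are nested in teams, and the providers of a team are always allocated together. A model whose highest level is the provider counts them as separate, independent units for the treatment comparison. If 12-month weight change is correlated across providers of one team, the standard error of the arm contrast is understated.

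Such correlation is plausible but not shown. In the GEM arm the coach is to "Communicate potential barriers/concerns to the team at baseline visit and as needed throughout the intervention period", and in the control arm "Patients will follow-up with their primary care teams as needed". Both point to care organised by team.

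This matters because the mixed model is the only planned comparison of patient outcomes between arms that handles any clustering. Once the unclustered tests are set aside, as they should be, it is the analysis a reader would rely on.

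**Working it through.** **The plan's own figure.** The only sample-size arithmetic that can be reproduced is attrition: 384 / 0.75 = 512, as stated. No ICC, SD, effect size, alpha or power is given, so every ICC below is an assumption.

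**Inputs.** T = 19 teams (sections III and VI); N = 384 patients at 12 months (section III), or 384 / 19 = 20.2 per team; P = 28 providers (section III, 28 / 19 = 1.5 per team), or 19 × 2 = 38 to 19 × 3 = 57 (section VI).

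**Closed form.** Let r be the team ICC, total variance 1, with no separate provider variance. For equal-sized units:

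- true variance of the arm contrast ∝ r/T + (1 − r)/N
- variance implied by the provider-only model ∝ r/P + (1 − r)/N

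At r = 0.05 the true value is 0.05/19 + 0.95/384 = 0.002632 + 0.002474 = 0.005106.

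- P = 28: 0.001786 + 0.002474 = 0.004260; SE ratio = √(0.004260/0.005106) = 0.913
- P = 57: 0.000877 + 0.002474 = 0.003351; SE ratio = √(0.003351/0.005106) = 0.810

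At r = 0.02 the ratios are 0.952 and 0.897. Since P exceeds T on every count, the ratio is below 1 whenever r > 0.

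**Simulation.** There were 40,000 null trials per setting, with stratified blocks of four, 20 to 21 patients per team and providers spread evenly over teams. The outcome was 12-month change, fitted by REML with arm and healthcare system as fixed effects. The table shows how often a nominal 95% interval excludes the true value when all correlation is at team level and equal in both arms, the case least favourable to the plan. Provider-only intervals use t on providers minus 3 df.

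| Team ICC | Provider-only, P = 28 | P = 38 | P = 57 | Team effect, Satterthwaite |
|---|---|---|---|---|
| 0 | 3.2% | 3.7% | 3.9% | 2.7–2.8% |
| 0.01 | 4.3% | 5.0% | 5.7% | 3.5–3.6% |
| 0.02 | 5.3% | 6.0% | 7.3% | 3.9–4.2% |
| 0.05 | 7.0% | 9.3% | 11.2% | 4.7–4.9% |

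A t-test on team mean changes gave 4.8–5.1% throughout. Simulated SE ratios for the provider-only model were 0.97 and 0.92 (P = 28) and 0.90 and 0.80 (P = 57) at ICC 0.02 and 0.05, close to the closed form.

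**Variations on the provider-only model** (P = 28 / 38 / 57 unless stated):

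- Normal reference: 6.5 / 7.0 / 7.9% at 0.02; 8.4 / 10.3 / 12.0% at 0.05.
- Correlation split equally between team and provider: 4.7 / 5.2 / 5.9% at total 0.02; 6.0 / 7.1 / 8.0% at 0.05.
- Team ICC in the GEM arm only: 4.5 / 4.9 / 5.7% at 0.02; 5.8 / 7.1 / 8.4% at 0.05.
- Correlation at provider level only: 4.2–4.9%, no excess.
- Sixteen teams (8/8 split assumed; P = 28 / 32 / 48): 6.1 / 6.7 / 7.6% at 0.02; 8.9 / 9.7 / 12.0% at 0.05.
- Team sizes from 0.5 to 1.5 times the mean (P = 28 / 57): 5.8 / 7.4% at 0.02; 7.8 / 11.6% at 0.05.
- Kenward-Roger in the least favourable setting at 0.05: 6.7% (P = 28) and 11.2% (P = 57). A small-sample correction at the wrong level does not repair the omission.

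**The case against.** The strongest reply concerns size. At the one provider total stated outright, 28, the provider-only model gives 4.3% and 5.3% at ICC 0.01 and 0.02. A team random effect is no better calibrated there (3.5–3.6% and 3.9–4.2%) and has wider intervals. That stands. Only the team-mean analysis stays near 5% at low ICC.

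The 57-provider column is also doubtful. Table 2 lists 28 providers for the 11 VA Manhattan teams, fewer than the 33 that three per team would need, so the ceiling is 28 + 8 × 3 = 52. The worst case softens only slightly: simulations with 52 providers gave 6.4–7.1% at ICC 0.02 and 10.7% at 0.05. The stated total of about 28 equals the VA Manhattan row alone, so the low end is uncertain too.

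The simulated model is of 12-month change, whereas the plan keeps baseline among the repeated outcomes and does not say what form the provider effect takes. If it is an intercept constant over visits, it cancels from the change contrast, and the percentages above do not describe that model. The model would then allow for even less clustering in the contrast, so this does not rescue the plan.

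Finally, counselling is given by individual providers and calls by coaches, which does not itself show correlation across a team's providers. This is fair, and is why the claim is conditional. But the plan should not rest on an unstated assumption that the team ICC is zero.

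**Conclusion.** The concern holds as a conditional statement. The randomised unit is missing from the model's correlation structure, and the intervals are too narrow whenever the team ICC exceeds 0, before any allowance for the reference distribution. That the team is omitted is certain from the text. How much it matters is not, because it depends on the team ICC, the number of providers per team and the reference distribution, and the documents settle none of these.

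With 28 providers and a t reference there is little or no excess error up to ICC 0.02. With two to three providers per team and ICC 0.05, error is roughly double the nominal 5%. If correlation sits only at provider level, there is no excess. The point should be fixed, but it ranks below the unclustered Mann-Whitney and Fisher tests in the same section, which are the larger problem.

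**What to change.** In the Data Analysis section, bring the team into the model so that it reaches the 12-month treatment contrast, by one of these routes:

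- **Change or follow-up weight as outcome.** Use baseline weight as a covariate and a team random effect, with provider nested in team if estimable. ANCOVA with a team effect and t on 16 df gave 2.8 / 3.5 / 4.2 / 4.7% error at ICC 0 / 0.01 / 0.02 / 0.05.
- **Baseline kept in the outcome vector.** Use a team-by-visit random effect, since a visit-constant intercept cancels from the change. With t on 16 df this gave 2.7–2.9 / 3.5–3.9 / 3.6–3.9 / 3.8–4.1%.
- **Team mean changes adjusted for healthcare system.** Analysis at team level was nearest to 5% in every setting simulated.

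Include healthcare system, the randomisation stratum, as a covariate. State the degrees-of-freedom method: Satterthwaite or Kenward-Roger for the team effect, or a fixed t on teams minus 3 (16 with 19 teams). State the ICC assumed. Reconcile the team count (16 or 19) and the provider count (about 28, or two to three per team), because both the df and the size of the problem depend on them.

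The cost is SAP wording and a changed random-effect specification, with no new data. Compared with provider-only intervals on a t reference, team-level Satterthwaite intervals average 4–9% wider at ICC 0, 5–13% at 0.01, 7–17% at 0.02 and 11–31% at 0.05, from 28 to 57 providers. They are somewhat conservative near ICC 0; the team-mean analysis is not.

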The GEM intervention has great potential to improve the delivery of obesity counseling within the PCMH model of primary care. Initial findings from an ongoing pilot study of this intervention among Veterans and PC staff at a VA medical center demonstrated that it was feasible and acceptable to Veterans and staff and facilitated goal-setting conversations (see Preliminary Studies). However, there is no standard by which to leverage the Patient-Centered Medical Home model to provide weight management care. There is a need to test weight management interventions within patient-centered medical homes that integrate and/or partner with effective, intensive programs such as MOVE! and DPP.

[name] (Co-I) has over three decades of experience leading multicenter and investigator-initiated lifestyle trials for diet, obesity, and exercise whose work in Diabetes Prevention Program (DPP), DDP-Outcomes Study and Women's Health Initiative has shaped national health guidelines.⁵²⁻⁵⁶

Study Design

We will conduct this study using 3 steps:

1. Test the impact of the GEM Intervention on weight change, and clinical and behavioral outcomes.
 - a. We will obtain weight and height measurements, waist circumference measurements, , and blood pressure measurements from patients at multiple time points throughout the study. We will also use questionnaires to measure dietary outcomes and physical activity outcomes. Finally, electronic health records (EHR) and surveys will be utilized to evaluate attendance to intensive weight management programs. ^{85, 96, 86, 97, 98, 99, 100, 101, 102}
2. Identify predictors of weight loss in the GEM intervention arm related to: a) goal-setting processes and b) intervention components.
 - a. We will measure attainment of behavioral goals by asking patients to report on how many days in the past week they achieved each of their SMART goals. ⁸⁸ We will record the number of telephone coaching calls received by patients within the research study database and measure the frequency of counseling by running a clinical reminder report and conducting electronic chart reviews.
3. Determine the impact of the GEM intervention on obesity-related counseling practices and attitudes in primary care providers.
 - a. We will survey providers to measure 5As-related competency and attitudes about weight loss using validated survey items. ¹³ The feasibility and acceptability of the intervention will be evaluated using RE-AIM analysis.

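### Aim 2 sets no time order between coaching calls or goal attainment and weight change, so its regression cannot support talk of effects; separately, its named models have no team or provider term

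*Combined protocol and SAP*

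**What the plan says.** Aim 2 looks for predictors of weight loss within the GEM arm, under two heads: goal-setting processes and intervention components. Step 2 of Study Design lists the measures: self-reported days in the past week on which each goal was met, frequency of counselling, and calls ("We will record the number of telephone coaching calls received by patients within the research study database").

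Under Telephone Coaching, "we will incorporate 12 telephone coaching calls by a health coach over 12 months", and the timetable is explicit: "Scheduled calls will occur every 2 weeks (biweekly) for months 1–3, monthly for months 4–6, and every other month (bimonthly) for months 7–12".

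The Aim 2 paragraph of Data Analysis and Data Monitoring starts with scatterplots and Spearman correlations "to display the association between weight change and potential predictors". It then goes further: "Multivariate regression models will be used to examine the effects of those predictors". On the model family it says: "Multivariate linear regression models will be considered for continuous outcomes and multiple logistic regression models will be considered for binary outcomes". Inverse-probability weighting is mentioned, but only for missing data.

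The paragraph gives no time point for weight change, no window for counting calls or goal attainment, no adjustment for interim weight, no list of confounders and no cluster term. The Aim 1 paragraph just before it states "The primary outcome is mean weight loss at 12 months" and has a mixed model that allows for correlation of patients within providers.

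**The concern.** There are two separate problems.

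**Time order.** Calls received and goal attainment arise after randomisation, while weight is changing. A patient who is losing weight has more reason to take the next call, and one who is not may stop answering. A motivated patient may both take more calls and lose more weight. In either case a regression of weight change on total calls can show a slope when calls do nothing. If that slope is reported as an effect, the trial could be read as showing which component to fund or expand.

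**Clustering.** GEM patients come from a small number of randomised teams. A linear or logistic model without a team or provider term treats them as independent, and its standard errors can be too small. How much this matters depends on how far the predictor itself varies between teams.

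**Working it through.** **1. The plan's own figures.** Number of Subjects gives 384 completers at 75% retention: 384/0.75 = 512 enrolled, as stated. The call timetable gives 6 + 3 + 3 = 12 calls, as stated, with 6 + 3 = 9 due by month 6. Methods and Procedures gives 19 teams. Taking the GEM arm as half: 384/2 = 192 completers, 19/2 = 9.5 teams and 192/9.5 = 20.2 patients per team. The documents supplied give no sample size, SD or ICC for Aim 2.

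**2. Time order.** Calls run to month 12 and the trial's weight outcome is at month 12. Nothing in the Aim 2 paragraph places the predictors before the outcome. Weight is due at baseline and at 6, 12 and 24 months (Data Collection), so ordering them is possible.

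**3. Feedback from weight to calls; true call effect zero.** Assumptions, none from the documents: 12-month SD of 5 or 7 kg, mean loss 2 kg, about 70% of calls taken, weight following a random walk. The log-odds of taking the next call are 0.85 + ln(OR) × (kg lost so far minus its expected value). There were 2,000 runs of 192 patients. Twelve-month loss was regressed on total calls. Cells show kg per call and the share of runs with p < 0.05.

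| SD | OR 1.00 per kg | OR 1.05 | OR 1.10 | OR 1.20 |
|---|---|---|---|---|
| 5 kg | 0.00 (5%) | 0.35 (36%) | 0.66 (87%) | 1.02 (100%) |
| 7 kg | 0.02 (4%) | 0.68 (59%) | 1.19 (99%) | 1.59 (100%) |

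Without feedback there is no bias, so the feedback produces it.

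**4. Does a 6-month landmark solve it?** In the same runs, weight change from month 6 to 12 regressed on calls to month 6 gives slopes within 0.02 kg of zero and 4% to 6% rejection. That is expected, because weight changes after month 6 are independent of earlier ones in this model. Two harder cases used 1,000 runs, SD 5.5 kg, half the variance from patient-specific slopes, and adjustment for month-6 weight:

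- *Shared motivation, no feedback, no true effect.* Call uptake depends on the same trait as the weight slope (log-odds 0.5 or 1.0 per SD). The landmark slope is 0.49 or 0.58 kg per call, significant in 92% of runs or more.
- *A true immediate effect of 0.3 or 0.5 kg per call.* The landmark slope is about -0.10 to -0.18 kg per call. The benefit of early calls is already in the month-6 weight. Of two patients with the same month-6 weight, the one who took more calls has the less favourable underlying slope.

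**5. Clustering.** Design effect = 1 + (m - 1) × ICC of outcome × ICC of predictor, with m = 20.2. Actual type I error of a nominal 5% test = 2[1 - Φ(1.96/√design effect)]. ICCs are assumptions: 0.01 to 0.05 for the outcome.

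- Patient-level predictor, ICC 0.05 to 0.3: from 1 + 19.2 × 0.01 × 0.05 = 1.01 to 1 + 19.2 × 0.05 × 0.3 = 1.29. Type I error is about 5% to 8%.
- Predictor varying only by team, ICC 1: from 1 + 19.2 × 0.01 = 1.19 to 1 + 19.2 × 0.05 = 1.96. Type I error is about 7% to 16%.

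The introduction gives 16 teams, not 19. With 8 GEM teams, m = 24 and the second range becomes 1.23 to 2.15.

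**The case against.** The best defence is that Aim 2 is exploratory. Its heading speaks of predictors, the first step is scatterplots and rank correlations, the predictors are described as suspected associations, and *effects* is common regression shorthand. This has force as to intent. But the regression is a separate step from the descriptive work, and nothing in the paragraph stops its coefficients being read causally. Replacing the word settles the matter at almost no cost.

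Second, the paragraph does not say that 12-month loss will be regressed on 12 months of calls. It says only weight change. That is correct: the overlap is the natural reading of Study Design, Telephone Coaching and the primary outcome taken together, not a written specification. What is established is that no order is set.

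Third, the size of the bias is driven by the assumed link between weight lost and call uptake, on which the documents have no data. This also stands, so the table shows what can happen, not what will.

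Fourth, the predictors named in Study Design are patient-level, for which the clustering error is small. That stands too. The larger figures apply only if a predictor varies mainly by team.

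Finally, a landmark model can miss a real effect and leaves motivation uncontrolled. Step 4 of the working bears this out, so it should not replace the planned analysis.

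**Conclusion.** The point holds in a limited form. The Aim 2 regression sets no order between calls or goal attainment and weight change, so it cannot separate an effect of coaching from weight already lost or from motivation. Under the assumed feedback, the false slope is 0.35 to 1.59 kg per call. Separately, no team or provider term is named. The consequence is minor for calls and larger for any predictor that follows team lines, at ICCs that are assumptions.

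A reader might infer four stronger things that the documents do not support:

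- *That a false coaching effect is certain.* It needs feedback or shared motivation, and the documents give no data on either.
- *That the missing cluster term causes the false effect.* It affects standard errors only, and a random intercept would not remove reverse causation.
- *That a landmark model cures the problem.* It removes feedback from earlier weight loss and nothing else.
- *That the trial's main result is in doubt.* Aim 2 is a secondary analysis within one arm, and the randomised comparison does not depend on it.

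The change is worth making before analysis, as a should rather than a must.

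**What to change.** 1. Add a random intercept for team to the Aim 2 models, and for provider if it can be estimated. Use small-sample degrees of freedom, because the GEM arm has only about 9 to 10 teams. If the inverse-probability weights make a mixed model awkward, use weighted regression with small-sample cluster-robust standard errors.
2. Replace *effects* with *associations* in the Aim 2 paragraph. State the outcome time point and the window for each predictor. Report the full-period call and goal-attainment results as descriptive only.
3. Optionally, as a sensitivity analysis only, add a 6-month landmark model: calls and goal attainment in months 0 to 6 as predictors, weight change from month 6 to 12 as outcome, adjusted for baseline and month-6 weight, with the same team term. State its limits with the result. It removes feedback from earlier weight loss but not confounding by motivation. It excludes any benefit of early calls already present at month 6, and it does not count the three later calls.

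The cost is a few sentences in the analysis plan and, for item 3, one extra model. The weight and call data are already due to be collected. Item 3 also needs goal attainment to be dated.
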